7.2.6 Study Medication

'Table 3: Study Treatments' shows the Study Treatments and how they will be labelled in all TLF outputs.

Table 3: Study Treatments

Treatment arm	Treatments
rhNGF	180 µg/ml rhNGF, one drop TID
Vehicle	Vehicle control, one drop TID

7.2.7 Primary Safety Outcomes

The primary safety outcomes of the study are:

Unexpected severe progression of optic neuropathy (USPON)

Unexpected Severe Progression of Optic Neuropathy will be measured a) by a central vision loss; b) by visual field testing; and/or c) by examination of the optic nerve. It is recorded per eye on the Follow-Up Visits of the eCRF pages 'Best Corrected Distance Visual Acuity', 'Humphrey Visual Field Monitoring', 'Electroretinography' and Ocular coherence tomography' via a tick box 'Was an unexpected severe progression measured...' (Yes/No).

USPON will be investigated only for treated eyes, i.e. if an eye is not treated, the respective tick box will not be considered for definition of primary outcome.

[figure not shown]
For a patient, USPON occurred, if in any of the following assessments the respective question on unexpected severe progression is answered 'Yes':

- a) from BCDVA assessments: eCRF question is ticked 'Yes' for at least one treated eye at any Follow-Up Visit after first study treatment administration (including unscheduled visits).
- b) from HVF assessments: eCRF questions is ticked 'YES' for at least one treated eye in at least one assessment during Treatment or Follow-Up Period (i.e. performed after first study treatment administration). An assessment is considered as performed during Follow-Up Period, if Test Date and Test time as documented on eCRF Page 'Humphrey Visual Field Monitoring' was after Week 8 Visit (See also Section 7.2.9 for Details).
- c) from ERG assessments: eCRF question is ticked 'Yes' for at least one treated eye at any Follow-Up Visit after first study treatment administration (including unscheduled visits).
- d) from OCT assessments: eCRF question is ticked 'Yes' for at least one treated eye at any Follow-Up Visit after first study treatment administration (including unscheduled visits).

As supportive variable, the occurrence of USPON during Treatment Period will be derived, which is defined as an USPON, which was recorded between the first study treatment administration and Week 8 Visit/Study termination Visit (for patient withdrawn during the treatment period).

Intolerance or allergy to the drug

The occurrence of intolerance and allergy to the drug will be identified during the BDRM by reviewing reported Preferred Terms of Treatment Emergent Adverse Events (for definition see Section: 7.2.10).

Adverse events affecting ocular function or eye pressure, which differ from those expected in the course of glaucoma, which are thought to be potentially related to the drug (Unexpected Related AEs affecting ocular function/eye pressure)

The occurrence of these events will be identified via the respective question on the AE form. It is expected, that only adverse events, which are occurring during treatment period, will be flagged for this endpoint by the investigator. So, no separate analysis is foreseen by study period.

Local or systemic toxicities considered serious adverse events that are potentially related to the drug

The occurrence of local and systemic toxicities will be identified via the respective question on the AE form. It is expected, that only adverse events, which are occurring during treatment period, will be flagged for this endpoint by the investigator. So, no separate analysis is foreseen by study period.

7.2.8 Primary Tolerability Outcome**VAS Ocular Tolerability Score**

Visual Analogue Scale (VAS) will be used to determine ocular tolerability to the study medication. It will be assessed by the patient using a self-administered 100 mm VAS on which 0 means no symptoms and 100 means the worst possible discomfort in either eye. This evaluation is to be performed before any ophthalmic examinations.

The VAS Ocular tolerability scores will be collected on the eCRF page 'Visual Analogue Scale Ocular Tolerability' per eye for the symptoms:

- 1) foreign body sensation
- 2) burning/stinging
- 3) itching
- 4) ocular pain
- 5) sticky feeling
- 6) blurred vision
- 7) photophobia

The Overall VAS Ocular Tolerability Score is the mean of all VAS Ocular Tolerability symptom scores per visit per eye. In case of missing symptom scores, the mean will be calculated on the remaining VAS scores if at least 5 out of 7 scores are non-missing.

Change from baseline is derived for overall score as well as for all 7 symptom scores will be derived as the difference between the respective values at a scheduled Follow-Up and Baseline Visit.

[figure not shown]
7.2.9 Exploratory Secondary Efficacy Outcomes

The following examination/procedures will be performed on both eyes and results and derived values as defined below in this section will be derived for each eye individually.

Changes in Best-Corrected Distance Visual Acuity

Vision must be measured using ETDRS visual acuity chart at 4 meters (13 feet) and, if indicated, also at 1 meter (i.e. when less than 20 letters were read at 4m). Results are documented on the eCRF page 'Best Corrected Distance Visual Acuity'.

In case both tables on the eCRF page have been completed (at 4 meter and at 1 meter) then the visual acuity score is the sum of the total number of correct letters from both tables. If only the table at 4 meter is completed and the overall number of letters read is 20 or above then the Visual Acuity Score is the number of total letters read at 4 meter plus 30.

If no letter were read at 4 and 1 meter, the best visual potential ability of the patient is selected from: a) count fingers; b) hand motion; c) light perception; or d) no light perception. The Visual Acuity Score is then set to 0.

The Snellen Equivalent is defined as the acuity equivalent for the smallest line with 1 or no error. The logarithm of the minimal angle of resolution (logMAR) is calculated as “- log (Snellen Equivalent)” with two decimals precisions. The logMAR ranges from 0.30 (20/10) to 1.60 (20/800) and an increase in logMAR reflects a worsening of visual acuity. If for a patient only ability for counting fingers is reported, logMAR will be set to 2.00; if for a patient only recognition of hand motion is reported, logMAR will be set to 3.00 (Holladay 1997).

For Visual Acuity Score and logMAR, change from baseline will be calculated as difference for Week 8, Week 12 and Week 32 Visit.

For safety evaluation, also the incidence of Substantial Worsening of Visual Acuity during Treatment will be derived at each Follow-Up Visit. A Substantial Decrease of Visual Acuity during Treatment is defined as:

- Decrease in BCDVA score of more than 30 compared to Baseline or
- Increase in LogMar of more than 0.6 compared to the Baseline or
- Decrease of Visual Acuity from at least Hand Motion to the Level of Light Perception or worse compared to Baseline

at any assessment (scheduled and unscheduled) after first Study Drug Administration up to and including Week 8 Visit.

A similar derivation will be performed for the incidence of Substantial Worsening of Visual Acuity during Follow-up Period considering all Assessments after Week 8 and Last Study Visit during the Follow-Up Period.

It needs to be noted that a Substantial Worsening of Visual Acuity as defined here will not necessarily implies an adverse event of special interest (AESI) or an USPON, as this definition is addressing a general worsening compared to start of study, whereas AESI and USPON are considering substantial changes from the last observed visit.

[figure not shown]
Changes in Visual field using Perimetry

Visual fields will be evaluated using static (Humphrey) perimetry and results are on the eCRF pages ‘Humphrey Visual Field Monitoring’ and ‘Humphrey Visual Field’. Two perimetries will be performed on different days for a total of 3 before initiating treatment and these will be reported as Baseline assessments. During treatment 3 assessments will be performed within 4 weeks. During follow up 3 perimetries will be performed within 4 weeks.

Humphrey Visual Field testing will be performed using SITA Standard. If a patient has a low vision and cannot perform the test via SITA Standard, the test is performed with the FASTPAC Standard. On the eCRF it is recorded which test type has been used.

All HVF assessments will be assigned to the respective study period according to the following rules:

- Screening Period: Date/Time of HVF assessment will be before Date/Time of First Study drug administration as documented on eCRF Page ‘Administration of Study Drug’
- Treatment Period: Date/Time of HVF assessment on/after Date/Time of First Study Drug Administration (as documented on eCRF Page ‘Administration of Study Drug’ and on/before Date of Week 8 Visit. If a patient did not perform a Week 8 Visit, all assessments after first Study Drug Intake will be assigned to the Treatment Period.

- Follow-up Period: Date/Time of HVF assessment after Date of Week 8 Visit.

Based on this assignment, the occurrence of USPON assessed via HVF will be determined.

Electroretinography (ERG)

A full field and pattern ERG will be performed according to international standards. On the eCRF page 'Electroretinography' only the PhNR result will be recorded in format 5.2 and used for statistical analysis.

For PhNR, the change from baseline will be calculated as differences for Week 8, Week 12 and Week 32 Visits.

Optical Coherence Tomography (OCT)

Spectral domain OCT acquisitions of macula and optic nerve head will be performed to evaluate changes in ganglion cell layer and nerve fiber layer thickness.

Retinal nerve fiber layer (RNFL) Thickness (μm , format 6.2) is recorded in the eCRF page 'Ocular Coherence Tomography' as follows:

- four RNFL Quadrants, namely superior (S), nasal (N), temporal (T) and inferior (I)
- twelve RNFL Clock Hours (1 to 12)
- average RNFL Thickness as measured by the OCT machine

From PanoMap analysis, Macular Thickness (μm , format 6.2) is recorded in the eCRF page 'Ocular Coherence Tomography' as follows:

- nine Areas, namely superior of outer ring (SOM), nasal of outer ring (NOM), inferior of outer ring (IOM), temporal of outer ring (TOM), superior of inner ring (SIM), nasal of inner ring (NIM), inferior of inner ring (IIM), temporal of inner ring (TIM) and central subfield thickness (CSF)

From Ganglion Cell OU analysis, Macular Cube Thickness (μm , format 6.2) is recorded in the eCRF page 'Ocular Coherence Tomography' as follows:

- six Areas, namely superior (SUP), superior temporal (ST), inferior temporal (IT), inferior (INF), inferior nasal (IN) and superior nasal (SN)

[figure not shown]
For all these variables, change from baseline will be calculated as differences for Week 8, Week 12 and Week 32 assessments.

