7.2.1 Disposition and Protocol Deviations

Disposition parameters are recorded on the eCRF Page ‘End of Study’.

[figure not shown]
Study discontinuations will be defined only for randomized patients.

A patient discontinued the study prematurely, if the question ‘Did the patient complete the study’ was answered as ‘No’. A patient is considered as study completer, if the question ‘Did the patient complete the study’ was answered as ‘Yes’. Otherwise the patient is considered as ‘Ongoing’.

Primary Reason for Study Discontinuation is documented on the eCRF Page ‘End of Study’ in categories ‘Adverse Event’, ‘Lost to Follow-Up’, ‘Decision unrelated to an Adverse Event’, ‘Non-Compliance’, ‘Study terminated by the sponsor’, ‘Study terminated by the investigator’, ‘Other’.

If the date of study discontinuation/study completion as documented on the eCRF page ‘End of Study’ is less or equal than 63 days after the date of first study drug administration as documented on eCRF Page ‘Study Drug Dosing Dates’, discontinuation will be considered as ‘During Treatment Period’, otherwise it will be considered as ‘During Follow-Up Period’.

A patient is considered as Completer of the Treatment Period, if he has a documented Week 8 Visit and did not discontinue the study during the treatment period.

If the eCRF question ‘Was the emergency envelope opened during the study?’ was answered ‘Yes’, the patient will be considered as unmasked.

Protocol deviations will be collected during the study and reviewed during the BDRM according to a separate BDRM plan. During the BDRM, identification of CSR reportable protocol deviations and further categorization of deviations for TLF output will be performed. For the analysis, the CSR reportable protocol deviations as documented in the BDRM minutes will be presented.

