7.2.5 Measurements of Exposure and Treatment Compliance

The patients will be dispensed a 4 week supply of study medication (1 kit) on the Day 0 visit and at Weeks 4.

Patients will also be instructed to bring back to the clinic at each study visit all the used and unused vials.

Each 4 week kit will be composed of 1 box containing a total of 90 single-use vials of the randomized / assigned medication for daily treatment during 4 weeks and 1 box containing the same number of adaptors and prefilled 0.3 ml WFI syringe.

[figure not shown]
All patients will be dosed one drop (35 µl) three times a day (TID) in each eye during the 8 weeks treatment period.

Exposure

Information on Exposure will be derived from information on eCRF Pages 'Study Drug Dosing Dates' (Date of First Study Drug Administration, Date of Last Study Drug Administration), 'End of Study' (Date of Study Discontinuation/Completion), 'Study Visits' (Date of Week 8) as well as 'Study Drug Dosing and Accountability' (Date of Vial Dispensed/Returned, Days without Treatment).

Exposure will be presented by displaying Duration of Treatment Period, Duration of Follow-up Period, Extent of Exposure and Days on Study Medication, which will be derived as follows

- Duration of Treatment Period:
Week 8 Visit Date or Date of Study Discontinuation/Completion – Date of First Study Drug Administration + 1, whatever is earlier.
- Duration of Follow-Up Period:
Date of Study Discontinuation/Completion – Date of Week 8, for all patients who have completed the treatment period and terminated the study (regularly or prematurely)
For patients who did not complete the treatment period, Duration of Follow-Up Period is set to 0.
Main Objectives Analysis only: if a patient has not completed the study yet, the last documented visit during Follow-Up Period (including unscheduled visits) will be considered for calculating Duration of Follow-Up Period.
- Extent of Exposure (days) = (Date of Last Study Treatment – Date of First Study Treatment Administration + 1),

If Date of Last Study Treatment is missing (e.g. due to Lost to Follow-Up), Date of Study Discontinuation/Completion or Date of Last Study Drug Return (as documented on the eCRF Page ‘Study Drug Dosing and Accountability’) will be used, whatever is earlier.

- Days on Study Medication = Sum of (Date of Vial Returned – Date of Vial Dispensation – Days without Treatment) +1 for all lines in eCRF Page ‘Study Drug Dosing and Accountability’.

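### For a patient who misses Week 8 but stays in the study, the SAP has no working end to the treatment period, so off-drug visual fields are labelled on-treatment

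*SAP*

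**What the plan says.** SAP 7.2.9 divides HVF assessments into screening, treatment and follow-up. Treatment begins with the first dose and ends on the date of the Week 8 Visit. For a patient without that visit the text reads: "If a patient did not perform a Week 8 Visit, all assessments after first Study Drug Intake will be assigned to the Treatment Period". Follow-up is defined only by reference to the same visit: "Follow-up Period: Date/Time of HVF assessment after Date of Week 8 Visit". The purpose is then stated: "Based on this assignment, the occurrence of USPON assessed via HVF will be determined".

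SAP 7.2.7 counts USPON for a patient from a tick on any of four sources after the first dose: visual acuity (BCDVA), HVF, ERG or OCT. It adds a supportive variable, USPON in the treatment period, for a progression "recorded between the first study treatment administration and Week 8 Visit/Study termination Visit (for patient withdrawn during the treatment period"). SAP 10.6.1 places both in the summary of primary safety outcomes (Table 14.2-1.1).

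Four other definitions touch the same patient:

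- **Treatment duration (SAP 7.2.5)** ends at "Week 8 Visit Date or Date of Study Discontinuation/Completion", whichever comes first. Follow-up duration is 0 for anyone who did not complete the treatment period.
- **Treatment completer (SAP 7.2.1)** is a patient who qualifies "if he has a documented Week 8 Visit and did not discontinue the study during the treatment period". An exit from the study falls in the treatment period if its date "is less or equal than 63 days after the date of first study drug administration".
- **SAF-F (SAP 6.1)** contains every patient in the safety set who had not terminated the study by Week 8.
- **Dosing (Protocol 8.2)** stops at Week 8, while Protocol 10.2.6 still schedules fields at Week 32.

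**The concern.** The HVF rule appears to have been written for patients who withdrew before Week 8. For them it is harmless, because no later fields exist. Its wording also covers a patient who misses the Week 8 Visit, stays in the study and returns at Weeks 12 and 32. For that patient the follow-up category is empty, and every later field belongs to the treatment period.

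What is at stake is one row of the primary safety table and some descriptive durations. The treatment-period row is the only planned split of USPON by time. Its use is to show which progressions arose on drug and which arose in the 24 weeks afterwards, and an off-drug event placed in it defeats that use. SAP 9.1 also lets primary safety data after Week 12 into the main objective analysis, while asking readers to concentrate on what was assessed before Week 12. A late field carrying a treatment-period label works against that advice.

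**Working it through.** The plan states no figure on this point to reproduce, and Protocol 11.4 has no formal sample size calculation. The check applies the SAP's definitions to an illustrative patient.

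**Inputs**

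- Week 8 window: 56 ± 7 days after first dose, i.e. 49 to 63 (SAP Table 2). The 63-day cut-off in SAP 7.2.1 equals 56 + 7.
- Week 12 window: 77 to 91. Week 32 window: 217 to 231, nominal 224 (SAP Table 2).
- Planned dosing: 8 weeks, so the last dose falls on treatment day 56.
- Supply: 2 kits × 90 vials = 180 vials (Protocol 9.1.2).
- Arms: 40 rhNGF and 20 vehicle, all assumed treated.

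**Patient: no Week 8 Visit, attends Week 12, completes at Week 32**

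1. *HVF period.* With no Week 8 date, all fields after first dose are treatment period, including those around Week 32. The visit-shifting rule in SAP 7.1 covers only patients who terminate during treatment, so it does not correct this.

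2. *Is Week 32 off drug?* Used at 3 vials a day, 180 vials last 180/3 = 60 days. At 1 vial a day they last 180 days. The documents can be read either way, and Week 32 begins at day 217, beyond both.

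3. *Duration of treatment period.* The formula is end date − first dose date + 1. Without a Week 8 date, only the completion date is left. Off-drug days are the duration − 56.

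| Week 32 on day | Duration (days) | Off-drug days | Share |
|---|---|---|---|
| 217 | 217 + 1 = 218 | 218 − 56 = 162 | 74.3% |
| 224 | 224 + 1 = 225 | 225 − 56 = 169 | 75.1% |
| 231 | 231 + 1 = 232 | 232 − 56 = 176 | 75.9% |

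4. *Duration of follow-up.* The patient has no Week 8 Visit, is therefore not a treatment completer, and is given 0 days.

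5. *SAF-F.* The patient had not terminated by Week 8 and so is included. The same person has entered follow-up under 6.1 and spent no time in it under 7.2.5.

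6. *BCDVA, ERG and OCT.* SAP 7.2.7 ends the treatment-period variable at Week 8, or at the termination visit of a patient withdrawn during treatment. This patient has neither, so the end point is undefined and the programmer must choose one.

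7. *Effect of one case on the treatment-period row.* 1/40 = 2.5 percentage points in rhNGF; 1/20 = 5 points in vehicle.

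**With the period ended at day 63**

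Treatment duration is 63 + 1 = 64 days. Follow-up at the nominal Week 32 is 224 − 63 = 161 days, and 64 + 161 = 225, so the total is preserved. The Week 12 window opens at day 77, after day 63, so assessments made within the Week 12 or Week 32 windows fall in follow-up. With the last dose on treatment day 56, 64 − 56 = 8 off-drug days still count as treatment.

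**The case against.** The best case for leaving the text alone is that little depends on it. Overall USPON counts both periods, so the label cannot change it. The treatment-period variable is called supportive, SAP 8.2 plans no inference on the primary safety outcomes, and HVF values are only listed (SAP 3.6). The situation needs a patient who misses a visit with a ±7-day window, stays, has a late HVF progression ticked, and had no earlier on-treatment progression. Evaluability is reviewed blind before unmasking, and the HVF listing shows dates beside the derived period. All of this stands and limits the size of the problem. It does not remove it: the blind review may notice the missed visit, but the rule in 7.2.9 would still be applied as written.

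Three stronger readings are tempting, and the documents do not support them.

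- *Early stopping of the drops is hidden, because attending Week 8 makes a patient a completer.* Extent of Exposure runs to the last dose, and Days on Study Medication subtracts untreated days. Both are summarised by arm (Table 14.1-7.1) and exposure is listed by patient (Listing 16.2.5-1.1). Withdrawal of treatment for an adverse event has its own table. The completer label is used only for follow-up duration, and SAP 10.1 specifies no count of it.
- *The comparison between arms is biased.* Nothing suggests that missed Week 8 visits would differ by arm, and the concurrent vehicle group is subject to the same rule.
- *Treatment-period USPON from BCDVA, ERG and OCT has no upper limit.* The rule covering every later assessment applies to HVF alone. For the other three sources the limit is missing, which is different from unlimited, and by-visit results keep their nominal visit label.

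**Conclusion.** The HVF period rule is wrong as written for patients who miss Week 8 and remain in the study, and the neighbouring definitions contradict one another for them. The affected outputs are the supportive treatment-period USPON row in Table 14.2-1.1, the period label in the HVF listing, and the treatment and follow-up durations. Overall USPON and every planned test are unaffected.

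In size, such a patient has a treatment duration of 218 to 232 days for an 8-week treatment. One misplaced progression moves the supportive row by 2.5 points in rhNGF or 5 points in vehicle. This assumes that dosing ended on schedule, that all 60 patients were treated, and that the patient had no earlier progression within the treatment period. The documents do not say how many such patients to expect, and there may be none. The point merits correction because the rule feeds a primary safety table with small denominators and is cheap to repair.

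**What to change.** 1. In SAP 7.2.9, restrict the rule that assigns every later field to the treatment period to patients who terminated the study during that period.
2. For patients without a Week 8 Visit who remain in the study, end the treatment period at day 63 after first dose. This is the cut-off in SAP 7.2.1 and the upper Week 8 limit in SAP Table 2.
3. In SAP 7.2.7, apply the same end to treatment-period USPON from all four sources: BCDVA, HVF, ERG and OCT.
4. In SAP 7.2.5, use it as the end of treatment duration and the start of follow-up duration for these patients, instead of setting follow-up to 0. This agrees with their membership of SAF-F.

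The definition of a treatment completer can stay as it is; no last-dose threshold is needed.

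The cost is a few sentences and a small extra derivation from dates already collected. The drawback is that some days after the last dose still count as on-treatment: 8 if dosing ended on treatment day 56.
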